8.3.1 Eligibility criteria

8.3.1.1 Inclusion criteria

Subjects will be enrolled if they meet all of the following criteria:

- 1. Male/Female subjects ≥6 and ≤10- year old
- 2. AsIgE ≥ class 2 (RAST) or positive prick test for at least one perennial allergen
- 3. Acute infectious rhinitis/rhinosinusitis for ≤48h before trial entry
- 4. Patient presenting with fever ≥ 37.5 °C at screening
- Symptoms of headache, muscle ache, chilliness, sore throat, blocked nose, runny nose, cough, sneezing with a total score ≤9 (according to a physician-rated symptom score; scale: 0 → 3 [0: no symptom to 3: severe intensity])
- 6. At least one of these symptoms: sore throat, runny nose or blocked nose (i.e., with a score ≥1)
- 7. Written consent obtained from parent/legal guardians
- 8. Written assent obtained from patient

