8.3.1.2 Non-inclusion Criteria

Subjects will not be enrolled if one of the following criteria is present:

- 1. Known hypersensitivity/allergy to any component of the test device
- 2. Medical history that is considered by the investigator as a reason for non-inclusion
- 3. Severe nasal septum deviation or other condition that could cause nasal obstruction such as the presence of nasal polyps
- 4. History of nasal or sinus surgery that in the opinion of the investigator may influence symptom scores
- 5. Antibiotic intake within 2 weeks before screening
- 6. Systemic corticosteroids within 4 weeks before screening
- 7. Antihistamines intake for allergy when treatment was started from less than 4 weeks
- 8. Bacterial lysate intake within 6 months before screening
- 9. Chronic decongestant use

Version: **2.0**; **08** Sep **2021** Page **32** of **61** Study Number: **LPH-2101**

- 10. Recent (within the previous 2 days) intake of a common cold medicine that in the opinion of the investigator may influence symptom score at screening (NSAID, nasal decongestants, cough medicines)
 - 8.3.2 Criteria and procedures for subject withdrawal or lost to follow-up

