8.3.11 Study procedures

The study will comprise 3 visits and 2 telephone calls.

Version: **2.0**; **08** Sep **2021** Page **34** of **61**

Visit 1 (V1) - (Day 1): Screening/Inclusion

The investigator will give oral information relative to the study to parents/legal guardians and the participant. If both parents/legal guardians agree that their child participate in the study, they will receive the information sheet and will be also asked to give a written consent. In case one parent will not be available for the visit; he/she will be asked to confirm in writing that he/she agrees with the participation of the child in the study. Children will also receive an information specific to their age and will be invited to sign an assent by the investigator.

Each screened subject will be assigned a subject identifier number during screening. The subject identifier number will contain the site number and the subject number and will be assigned in numerical order at the screening visit based on chronological order of screening dates (e.g., 01-010 for the 10th subject screened at the Site #01).

The investigator or his/her delegated designee will:

- Record demographic data and medical history and ongoing medication,
- Perform a physical and clinical examination,
- Record the score of the common cold symptoms (headache, muscle ache, chilliness, sore throat, blocked nose, runny nose, cough, sneezing according a physician-rated symptom score after clinical examination of the child; (scale: 0 3 [0: no symptom, 1 = mild symptoms (sign/symptom clearly present, but minimal awareness; easily tolerated), 2 = moderate symptoms (definite awareness of sign/symptom that is bothersome but tolerable), 3 = severe symptoms (sign/symptom that is hard to tolerate; causes interference with activities of daily living and/or sleeping]). This scoring system was developed by Jackson in 1958 and is widely used in common cold clinical trials [19],
- Verify that eligibility criteria are fulfilled,
- Record the patient choice regarding Healsea® Children use (if the patient/parents choose nasal symptoms to be treated with Healsea® Children, instructions will be given to the patient/parents for getting the test product at the end of the visit),
- Explain to the child/parents/legal guardians how to use Healsea® Children if applicable,
- Review and detail the questions of the WURSS-K,
- Explain how to use the e-diary for WURSS-K recording, how to report adverse events/

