9.1 Descriptive statistics

The cohort is described: continuous variables will be summarized using the mean, standard deviation, median, minimum, maximum and quartiles, categorical variables will be summarized using frequency counts and percentages.

Two groups (called treatment groups for a sake of simplicity) will be extracted from the cohort according to the treatment chosen by the patient and a description of each group will be performed.

Details of the statistical analyses, methods and data conventions will be described in the SAP.

All statistical tests will be 2-sided and performed using a 0.05 significance level.

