10.2. Analysis of the secondary efficacy criteria

The analysis of the secondary endpoints will involve multivariate analysis.

The selection of variables in multivariate analysis will be performed using a 0.20 significance level and a stepwise method. Whole the multivariate analyses specified below involve the treatment and, in order to adjust for confounding, all the potential confounding factors as explanatory variables:

- Temperature at baseline (°C);
- Symptoms' scores at baseline.

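### The adjusted models omit maintenance antihistamine and nasal corticosteroid use, recorded at Visit 1, from a covariate list that the SAP presents as complete; residual confounding of unknown, probably small, size remains

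*SAP*

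**What the plan says.** **Group formation.** Protocol 9.1 forms the groups "according to the treatment chosen by the patient and a description of each group will be performed". There is no randomisation, and Protocol 8.1.2, on minimising bias, is marked as not applicable.

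**Adjustment.** SAP 10.2 says the multivariate models contain the treatment and, "in order to adjust for confounding, all the potential confounding factors as explanatory variables". It lists two: baseline temperature and "Symptoms' scores at baseline". It also says: "The selection of variables in multivariate analysis will be performed using a 0.20 significance level and a stepwise method".

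**Who can enrol.** Protocol 8.3.1.1 requires "AsIgE ≥ class 2 (RAST) or positive prick test for at least one perennial allergen". Protocol 8.3.1.2 excludes "Antihistamines intake for allergy when treatment was started from less than 4 weeks", so a child on an antihistamine for longer may enter. Among corticosteroids it names only systemic use. Protocol 8.3.12 authorises every concomitant medication except nasal irrigation in children who do not use the spray.

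**What is recorded and how it is used.** At Visit 1 the investigator must "Record demographic data and medical history and ongoing medication" (Protocol 8.3.11). SAP 8.2 summarises these medications by frequency and percentage. The note in SAP 10.3 counts a drug started before the reference start date and still ongoing as previous, not concomitant. None of the models in SAP 10.2.1 to 10.2.5 contains baseline medication.

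**Inferential status.** SAP 6.3.1 treats only the primary criterion as conclusive and everything else as descriptive. The primary test in SAP 10.1 is an unadjusted t-test or Wilcoxon test.

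**The concern.** In a self-selected comparison, an adjusted estimate is only as good as its covariate list. Every child here is sensitised to a perennial allergen, so some will plausibly be on maintenance allergy treatment. Whether a family adds a nasal spray could well depend on whether the child already takes an antihistamine or a nasal corticosteroid.

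Much of the link to outcome is in the protocol itself. Section 5 describes allergic rhinitis by its nasal symptoms, and section 8.1.4 includes topical corticosteroids among treatments that may affect cold symptoms. Runny nose, stuffy nose and sneezing are scored items in the primary AUC, and each has its own Cox model.

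At stake is how the adjusted results are read. The ANCOVA in SAP 10.2.1 is the only adjusted look at the primary endpoint, and it is run on both analysis sets. A reader told that every potential confounder is in the model will take it as such, while an obvious treatment variable in an allergic cohort has been collected and left out.

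**Working it through.** **The plan's own figure.** SAP 4 gives 100 per arm for a standardised difference of 0.4, 80% power and 5% type I error. With the normal approximation, n = 2 × (1.960 + 0.842)² / 0.4² = 98.1, so 99 per arm; the noncentral t gives 100. Power at 100 per arm is Φ(0.4 × √50 − 1.960) = 80.7% (80.4% with the noncentral t). The figure reproduces, and 0.4 SD is the yardstick below.

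**Share of the score.** Protocol 8.1.3 has 14 items scored 0–3, so 14 × 3 = 42 points a day. The three nasal items give 3 × 3 = 9 points. Of the six symptom items with a duration endpoint (items 2 to 7), three are nasal.

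**Bias from an omitted yes/no covariate.** Bias in SD of AUC = g × Δp, where g is the drug's effect on the total AUC in SD and Δp is the between-group difference in use. The documents give neither, so both are assumptions: Δp = 0.10–0.20, and g from one of two routes.

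*Route A: the drugs act only on the three nasal items, by δ = 0.3–0.5 SD each.* With 14 item AUCs of equal variance and common correlation ρ, the variance of the sum is 14 + 14 × 13 × ρ = 14 + 182ρ in item-variance units, so g = 3δ / √(14 + 182ρ). Take ρ = 0.2–0.6 (assumed).

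| ρ | √(14 + 182ρ) | g at δ = 0.3 | g at δ = 0.5 |
|---|---|---|---|
| 0.2 | 7.10 | 0.127 | 0.211 |
| 0.6 | 11.10 | 0.081 | 0.135 |

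Bias runs from 0.081 × 0.10 = 0.008 to 0.211 × 0.20 = 0.042 SD, which is 2% to 11% of 0.4.

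*Route B: the drugs shift the whole score by g = 0.3–0.5 SD.* Bias runs from 0.3 × 0.10 = 0.03 to 0.5 × 0.20 = 0.10 SD, which is 7.5% to 25% of 0.4. To reach this through the nasal items alone, each would have to move by g × √(14 + 182ρ) / 3, that is 0.3 × 7.10 / 3 = 0.71 SD to 0.5 × 11.10 / 3 = 1.85 SD. Route B is therefore an upper bound that needs very large item effects or action on other items such as sleep or breathing.

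**What the bias does to a test that ignores it.** With 100 per group and no device effect, the two-sided rejection rate is Φ(−1.960 + b√50) + Φ(−1.960 − b√50). For b = 0.042 this is 6.0%; for b = 0.10 it is 10.9%.

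**What baseline adjustment removes.** These figures are for a comparison without baseline adjustment. The physician-rated baseline scores (Protocol 8.3.11) include blocked nose, runny nose and sneezing, and are taken while the child is on any maintenance drug. They therefore carry part of g. They do not carry continued drug action over D1–D10 beyond what Day 1 severity predicts. The documents do not allow that split to be calculated.

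**Cost of adding a covariate.** For a yes/no covariate with mean prevalence 0.5 (assumed), the variance inflation is 1 / (1 − Δp²): 1.010 at Δp = 0.10 and 1.042 at 0.20. Power at 0.4 SD goes from 80.7% to 80.4% and 79.1%, before any gain from explained variance.

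**Medication outcomes.** SAP 10.2.4 counts topical corticosteroid use on any day from D1 to D30 and does not say whether use ongoing at baseline counts. If it does, a maintenance user scores yes whatever the cold does and can add up to 30 days to the count. A maintenance nasal corticosteroid covariate would then nearly determine the outcome in that model, and would come close to doing so among such users in the any-cold-medication model.

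**The case against.** The strongest reply is that the adjusted models already offer nasal symptom scores measured on treatment, and that excluding recently started antihistamines means users' scores reflect an established effect. This largely stands. A reader might infer that any imbalance in maintenance treatment carries over in full to the adjusted AUC; the documents do not support that, because only the part not captured at baseline can confound. The reply is weakened by the 0.20 stepwise rule, which may drop the baseline scores themselves.

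Second, the documents give neither the prevalence of maintenance treatment nor any link between it and choosing the spray. Entry requires sensitisation, not treated disease, and the list of symptom-affecting treatments in Protocol 8.1.4 does not name antihistamines. This stands: the confounding is plausible, not shown. Nor do the documents give a route from inhaled corticosteroids to the nasal items, so these should not be pooled with nasal ones.

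Third, these models are descriptive and the conclusive test is unadjusted. That also stands, and it limits the consequence. It does not excuse describing a two-item list as complete.

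Fourth, age, sex and centre are missing too. True, but this widens the gap and does not answer it.

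**Conclusion.** The point holds as one about residual confounding in the descriptive adjusted models. The covariate list is shorter than the SAP says, and a relevant baseline variable that has already been collected is left out.

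Its size cannot be derived from the documents. With assumed nasal-item effects of 0.3–0.5 SD, inter-item correlation of 0.2–0.6 and a 10–20 point imbalance, it is about 0.01–0.04 SD of total AUC before baseline adjustment. It reaches 0.10 SD only if the drugs move the whole score by 0.5 SD and the imbalance is 20 points. The direction could be either way. Adjusting for baseline scores should leave less than this. For the three nasal duration endpoints the effect is not diluted by the other items, but the documents give no basis for a figure.

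A reader might take the upper range, 7.5–25% of the planned effect, as the bias in the adjusted estimate. That would be wrong: it assumes no baseline adjustment and a large shift in a total of which only 3 of 14 items are nasal. A reader might also infer that extending SAP 10.2 would secure the trial's main conclusion. It would not, because the primary test takes no covariates.

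**What to change.** 1. In SAP 10.2, derive two yes/no indicators from Visit 1 ongoing medication: maintenance antihistamine and maintenance nasal corticosteroid. Add both to the AUC ANCOVA (SAP 10.2.1) and the six Cox models (SAP 10.2.2), exempt from stepwise removal.
2. Add them to the logistic and Poisson models only where event counts allow. The antibiotic-complication model may have few events.
3. Leave the nasal corticosteroid indicator out of the topical-corticosteroid and any-cold-medication models. In those, count only use newly started after Day 1, and say so in SAP 10.2.4.
4. Report the expanded models beside the planned ones as a labelled sensitivity analysis. SAP 12 describes how several patients had answered the questionnaire, so responses were already known when the SAP was written, and the addition should not be presented as if chosen blind to the data.
5. Replace the claim of completeness with wording that names the covariates used and admits that others may be missing. State that these models are descriptive under SAP 6.3.1 and do not protect the unadjusted test in SAP 10.1.

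The cost is a short SAP amendment, coding of existing medication records and extra output columns. No new data are needed. The ANCOVA uses two more degrees of freedom with about 200 children, and the power loss is about 0.3 to 1.6 percentage points per covariate under the assumptions above (80.7% to 80.4% or 79.1%).

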10.2.1. Modelling of AUC on total WURSS by multivariate ANCOVA

The analysis of the impact of the treatment chosen on the primary endpoint will be enriched by means of a multivariate ANCOVA model with the AUC of the WURSS-K during first ten days of symptoms as dependent variable. Subjects will be analysed on the Full Analysis Set and the Per-Protocol Set.

10.2.2. Impact of the treatment chosen on the cold symptoms' duration

Hereinafter, the “recovery date” is the first day of two last days the patient answered to the WURSS-K questionnaire. The patient must have reported a negative answer to the question 1 (“not sick”) and the two last days must be consecutive. Otherwise, there is no “recovery date” for the patient.

For the items 2 to 7 of WURSS-K questionnaire, the duration of the corresponding symptom is defined as the duration between first symptomatic day and last symptomatic day.

Cold symptom's duration (days) = Last symptomatic day – first symptomatic day + 1

For a given symptom, a symptomatic day is a day the patient gave an answer other than negative to the corresponding question (“do not have this”). Missing answers will be imputed by the last observation carried forward (LOCF).

The considered symptomatic days are between D1 and either D30, or the end of the study, or the day before the recovery date, whichever occurs first. Symptomatic days from the recovery date will not be taken into account.

For each of the items 2 to 7 of the WURSS-K questionnaire, the origin date will be the date of the first symptomatic day.

The considered event is the end of the symptom.

For patients who reported a negative answer to the corresponding question on the last day they answered to it, or for patients with a recovery date, the event date will be the last symptomatic day before his/her last day of completion of the questionnaire, or before the recovery date if it exists.

Patients who did not report a negative answer to the corresponding question on the last day they answered to it, and without recovery date, will be censored at D30 or at the end of the study, and the censoring date will be the date of D30 or the reference end date, whichever occurs first.

For patients who never reported the presence of a given symptom (never ticked “a little bad”, “bad” or “very bad”), if they completed the questionnaire at D1, then their origin date will be D1, they will be censored at D1 and their corresponding duration will be zero, else they will have neither origin date nor censoring date and the corresponding duration will be missing.

For each of the items 2 to 7 of the WURSS-K questionnaire, the impact of the treatment chosen on the corresponding cold symptom' duration will be analysed by means of a Cox model. Subjects will be analysed on the FAS.

10.2.3. Impact of the treatment chosen on the risk to develop respiratory complication requiring antibiotics prescription

The impact of the treatment chosen on the risk to develop respiratory complication requiring antibiotic prescription during a 20-day follow-up period will be analysed by a multivariate logistic model. Subjects will be analysed on the FAS.

10.2.4. Impact of the treatment chosen on the intake of a conventional cold medication

The impact of the treatment chosen on the intake of a conventional common cold medication will be analysed on the FAS.

Common cold medications are antibiotics, antipyretics, mucolytics, decongestants, antitussives, systemic and topical corticosteroids.

The use/non-use of these medications (if the patient used it at least one day from D1 to D30, or if he/she never used it) will be modelled by a multivariate logistic regression.

The number of days of intakes of these medications is defined as follows:

- A day is counted when the patient used at least one of these medications this day;
- Each day is counted once, whatever the number of these medications used this day;
- The total number is the sum of all distinct days of use of these medications, from D1 to D30.

The number of days of intakes of these medications will be modelled by a multivariate Poisson regression.

The same analyses will be performed for each category of medications: antibiotics, antipyretics, mucolytics, decongestants, antitussives, systemic and topical corticosteroids.

10.2.5. Impact of the treatment chosen on the number of family members in close contact developing common cold symptoms

The impact of the treatment chosen on the number of family members in close contact developing common cold symptoms after the patient all over the study period will be analysed by means of a multivariate Poisson regression. Subjects will be analysed on the FAS.

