The common cold is the most frequent upper respiratory tract infection (URTI), which is the most commonly treated acute problem in primary pediatric care [6]. Despite the usually benign nature of the illness, the common cold is an enormous economic burden on society in terms of visits to doctors, treatments, and absences from work, school, or day care [6][7]. The common cold is an acute viral infection of the upper respiratory tract, involving, to variable degrees, sneezing, nasal congestion and discharge (rhinorrhea), sore throat, cough, low-grade fever, headache, and malaise [2]. It can be caused by members of several families of viruses. However, rhinoviruses have been consistently found to be the most common cause in all age groups, irrespective of the viral detection techniques used. Yearly, rhinoviruses account for about 30-50% of all respiratory illnesses, but during the autumn peak season these viruses can cause up to 80% of all upper respiratory infections. Coronaviruses and Influenza viruses account for about 10-15% and for 5-15% of acute infectious rhinitis respectively. Other viruses such as Respiratory Syncytial Virus, Adenoviruses and Parainfluenza viruses are less involved [7]. Acute viral rhinitis is generally self-limiting. In children where the illness is not self-limiting and extends beyond 7-10 days, many agree that a bacterial infection is likely [2]. Acute bacterial rhinosinusitis is diagnosed in a child based on several criteria: persistent upper respiratory tract symptoms more than 10 days (cough or nasal discharge or both); or recurrence of symptoms after initial improvement: fever, worsening cough, or worsening or new purulent rhinorrhea; or severe onset of symptoms like fever or purulent nasal discharge lasting more than three consecutive days associated with facial tenderness or headache. Bacterial over infections and progression to a chronic condition are favored by the formation of biofilms, which facilitate bacterial growth and persistence as well as reducing antibiotic efficacy [8][9].

Allergic diseases may play a particular role in promoting the respiratory infection recurrences. The physiological immune response is impaired in allergic subjects and allergic inflammation favours predisposition to respiratory infections [10]. Subjects with allergic disorders may have functional defect of type 1 immune response that is relevant in fighting infections [11][12]. Allergic rhinitis (AR)

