6.4.6. AUC on total score of WURSS-K questionnaire

The computation of the AUC will be made for patients with non-missing value at D1 and at least another non-missing time point between D2 and D11. Otherwise, the AUC will be missing.

The AUC will be computed by the trapezoidal rule from D1 to D10 (Acute Phase).

If the value at D10 is missing:

- If there is no follow-up for the patient or if the value at D11 (the first day of Follow-up) is missing, then the value at D10 will be estimated by the value at the last non-missing time point before D10;
- If the value at D11 is not missing, the value at D10 will be estimated by a linear regression between the last non-missing time point before D10, noted Dj, and D11:

$$\text{WURSS}_{\text{TOT, EST}}(\text{D10}) = [\text{WURSS}_{\text{TOT}}(\text{Dj}) + (10 - j) \times \text{WURSS}_{\text{TOT}}(\text{D11})] / (11 - j)$$

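### Carrying the last symptom answer across missed diary days dates the symptom's end on the last missed day, which lengthens durations and, if gaps differ between groups, biases the hazard ratio

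*SAP*

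**What the plan says.** SAP 10.2.2 analyses the duration of each of WURSS-K items 2 to 7 with a Cox model on the Full Analysis Set. The rules that matter here are these.

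- Symptomatic day: "a symptomatic day is a day the patient gave an answer other than negative to the corresponding question".
- Missed days: "Missing answers will be imputed by the last observation carried forward (LOCF". A missed day therefore inherits the status of the last answered day.
- Duration: "Cold symptom's duration (days) = Last symptomatic day – first symptomatic day + 1".
- Event date: "the event date will be the last symptomatic day before his/her last day of completion of the questionnaire", or the last symptomatic day before the recovery date if there is one.
- Recovery date: the first of the last two diary days, provided they are consecutive and both are answered not sick on question 1. After that, "Symptomatic days from the recovery date will not be taken into account".
- A child whose last answer to the item is positive and who is "without recovery date, will be censored at D30 or at the end of the study" is not an event.

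The primary endpoint follows a different rule. SAP 6.4.6 states "The AUC will be computed by the trapezoidal rule from D1 to D10 (Acute Phase". With no other rule given for missed days between D1 and D10, an interior gap is bridged by a straight line between the answers on either side.

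Protocol 8.1.4 defines duration by what the child reports and does not mention LOCF. SAP 12 explains other changes to the duration definition but not this one. SAP 6.3.1 makes every result except the primary one descriptive, with p-values for information. The mock Table 14.2.2.2 nevertheless shows a hazard ratio, 95% confidence interval and Wald p-value for each symptom.

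**The concern.** A gap between a positive and a negative answer shows only that the symptom ended somewhere inside it. LOCF replaces that interval with its latest day and treats the day as observed. The resulting error in the child's duration is zero at best and otherwise positive.

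The hazard ratio is affected only if the groups differ in how often, or for how long, they miss days around recovery. That is possible. Treatment is open and chosen by the family (Protocol 8.2), and only Healsea families also report spray use (Protocol 8.3.11). A child who feels well has less reason to fill in the diary.

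Little in the plan would limit or reveal such gaps. The only completeness criterion (WURSS-K at D1, D5±1 and D10±1; Protocol 12, SAP 7.2) removes children from the Per-Protocol Set, while the Cox models use the Full Analysis Set. No comparison of diary completeness between groups is planned. At stake are six tabulated durations and hazard ratios that could partly reflect diary-keeping.

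**Working it through.** **Figures in the plan.** The documents give none for symptom duration, hazard ratio or diary gaps. The only related figure is the sample size for the primary endpoint: n = 2(1.96 + 0.84)²/0.4² ≈ 98, or 99 per group with unrounded quantiles. Exact t-test power at 100 per group is 0.804, so the stated 80% reproduces. The figure of 100 per group is used for the rejection rates below.

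**The rule in general.** Let the last positive answer be on day p and the next answer, negative, on day q. LOCF sets the end at q − 1. The answers allow any day from p to q − 1, so the overstatement lies between 0 and q − 1 − p days.

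**Traced diaries.**

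- Positive D1-D5, missed D6-D8, negative and not sick D9-D10. The recovery date is D9, and D6-D8 are filled as symptomatic. Duration = 8 − 1 + 1 = 8 days; the answers allow 5 to 8. The recovery date does not help, because it is an answered day and falls after the gap.
- Positive on D4, missed D5-D9, negative on D10. The last two diary days are not consecutive, so there is no recovery date. The event is on D9; the answers allow D4 to D9.
- Positive D1-D3, negative D4, missed D5-D8, not sick D9-D10. Duration is 3 days. A symptom that came back and ended inside the gap would be missed, so LOCF can also shorten an illness.
- Positive D1-D5, then no further entries. The child is censored at D30 or end of study. This is a separate case.

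**Simulation 1: gaps unrelated to recovery.** The SAP 10.2.2 rules were applied to diaries with identical true durations in both groups (mean 7, SD 2.5 or 4; mean 9, SD 3). Protocol 6.6 puts the illness at about 7-10 days; the SDs and all gap rates are assumptions. The hazard ratio is for symptom end, exposed against unexposed, from 12,000 per group. Rejection rates are from 600 trials of 100 per group at mean 7, SD 2.5.

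| Days missed, exposed vs unexposed | Null HR | p<0.05 |
|---|---|---|
| 10% vs 10%, scattered | 1.00 | 4.0% |
| 5% vs 15%, scattered | 1.03-1.04 | 6.0% |
| 5% vs 30%, scattered | 1.09-1.14 | 16.5% |
| 5% vs 15%, runs averaging 3 days | 1.07-1.12 | 10.2% |
| 5% vs 30%, runs averaging 3 days | 1.18-1.31 | 46.0% |
| 15% vs 5%, runs averaging 3 days | 0.89-0.94 | not run |

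The last row shows the bias reversing when the exposed group has more gaps. For 3-day runs at 5% vs 15-25% and mean durations of 7-8.5 days, the range is 1.07-1.25.

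**Simulation 2: a share of children skip from recovery until D10.**

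| True mean duration | 5% vs 15% skip: HR, p<0.05 | 5% vs 25% skip: HR, p<0.05 |
|---|---|---|
| about 5 days, none beyond D9 | 1.19-1.21, 20-23% | 1.39-1.42, 67-70% |
| 7 days, SD 2.5-3.5 | 1.05-1.08, 5-6% | 1.11-1.15, 14-21% |
| 8.5 days, SD 3 | 1.03, about 7% | 1.07, about 7% |
| 10 days, SD 3 | 1.00-1.01, 4-5% | 1.00-1.01, 4-5% |

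A further run over means of 7-8.5 days gave 1.01-1.17 with 8-18% rejection.

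The fall with duration is expected. A child whose symptom ends on day d and who returns on D10 gains 9 − d days. At d = 5 that is 4 days, so 5% and 25% skipping add about 0.05 × 4 = 0.2 and 0.25 × 4 = 1.0 days to the group means. At d = 7 it is 2 days.

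**Alternative end dates.** In simulation 1, placing the end midway between the last positive and first negative answer brings the null HR to 1.00-1.01 (scattered) and 1.01-1.04 (runs). Ending at the last positive answer reverses the bias, to 0.86-0.98. In a grouped proportional-hazards fit for the 5-day symptoms, LOCF against interval censoring gave 1.12 vs 1.00 (random gaps, 5% vs 25%), 1.24 vs 1.09 (skip 5% vs 15%) and 1.56 vs 1.23 (skip 5% vs 25%).

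**The case against.** **The gap rates are invented.** This stands. No completion rate appears anywhere. Both groups fill in the same daily diary apart from the spray entry, and there are optional reminders (Protocol 10.5), a telephone call at D5±2 and a diary review at Visit 2. Uneven gaps are possible, not shown.

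**The large values need favourable inputs.** This stands. A reader might infer from a hazard ratio near 1.4 and two-thirds of null trials significant that the rule will manufacture an effect. That result needs symptoms averaging about 5 days, none beyond D9, and children who skip from recovery to D10. A single symptom can be shorter than the illness, so 5 days is not excluded, but at 7-8.5 days the same behaviour gives 1.01-1.17.

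**LOCF does not always overstate.** This stands in part. If the symptom truly ended on the last missed day the duration is exact, and a relapse inside a gap that follows a negative answer is lost. For the gap described here, positive before and negative after, the error cannot be negative.

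**The endpoint is descriptive.** This stands and limits the severity. It does not remove the point, because the estimates themselves are affected and are tabulated with intervals and p-values.

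**The contrast with the AUC is partial.** This also stands: SAP 6.4.6 itself carries the last value forward to D10 when D11 is missing or there is no follow-up. The contrast holds only for interior gaps.

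**Conclusion.** The concern holds for gaps that a negative answer or the recovery date closes. The rule enters the latest possible end as if observed. With equal gaps it lengthens the durations in Table 14.2.2.2 and leaves the null hazard ratio at 1. With unequal gaps it biases the hazard ratio in either direction.

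For assumed gaps of 5% against 15-25%, the null hazard ratio is about 1.01-1.25 at mean durations of 7-8.5 days, and up to about 1.4 only for short symptoms with recovery-related skipping to D10. Scattered, mildly uneven gaps matter little.

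A reader might infer that the duration results are tilted towards Healsea, or that the primary result is affected. The documents support neither. They say nothing about which group misses more days, and the AUC has its own missing-data rule. A diary abandoned while the symptom is still positive falls under the censoring rule and is a different question. The change is worth making, but this is not a threat to the trial's main conclusion.

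**What to change.** In SAP 10.2.2, replace the LOCF end date with an interval-censored end.

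- Lower limit: the last day on which the item was actually reported present, taken before the recovery date if one exists.
- Upper limit: the day before the next answered day on which the item is reported absent after that last positive answer, or the day before the recovery date, whichever comes first.

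This definition copes with a symptom that pauses: present D1-D3, absent D4, present D5-D6 and absent D7 gives D6 to D6. It also copes with a child ended by the recovery date while the item is still positive. Fit a proportional-hazards model for interval-censored data.

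Report two sensitivity analyses: the LOCF end (upper bound) and the last reported positive day (lower bound). They bound each child's duration. They do not strictly bound the hazard ratio, since the true ends may lie nearer one limit in one group. Tabulate by group the number of children with a gap at the symptom end, so that readers can see whether the issue arose.

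Cost: SAP wording and one more model per symptom, with no new data. Confidence intervals will be slightly wider where gaps exist. Gaps caused by recovery itself are only partly corrected: in the simulated short-symptom case, 1.56 fell to 1.23, not to 1.
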